Document Date: 03/25/2019

The Effects of a Jump Rope Exercise Program on Vascular Health, Inflammatory Markers in Prehypertensive Adolescent Girls: full study protocol and statistical analysis plan

NCT#03534427

Study protocol

Participants

Forty girls (age 14-16) volunteered to participate in this research study. All participants were classified as prehypertensive (120-140 mmHg systolic BP and/or 80-90 mmHg diastolic BP) and had abdominal obesity (waist > 80 cm, BMI equal to or greater than the 95th percentile for age and sex). All participants were considered to be inactive, meaning they participated in less than 1 hour of regular physical activity per week within the last 6 months. Other exclusion criteria included a previous musculoskeletal injury within the last year that may negatively affect participation, as well as cardiovascular, pulmonary, adrenal, pituitary, and thyroid diseases. Participants who were already involved in a regular exercise program, on daily medication(s), including antioxidants and fat loss supplements, or weight loss diet plans were also excluded from participation. All procedures performed in this study were in accordance with the ethical standards of the institutional research committee at Pusan National University (PNU IRB/2016_105_HR) and with the tenets of the Declaration of Helsinki. This study was registered in Clinicaltrials.gov (NCT03534427). Informed consent was obtained from all individual participants and their parent/guardian(s) included in this study. Participant characteristics can be seen in Table 1.

Study design

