A two-armed, parallel experimental design was used. The jump rope exercise intervention took place during the months of March – June during the school year. Blood samples, anthropometrics, and vascular function parameters were assessed before (baseline) and after the 12-week jump rope exercise program at 8:00 AM (± 1 hour) following an overnight fast. After baseline measurements were performed, the participants were randomly assigned to either the jump rope exercise group (EX, n = 20) or the control group (CON, n = 20). The participants in the EX group participated in an exercise program (50 minutes per day, 5 times per week for 12 weeks) that consisted of jump rope variations. Exercise was performed at 2:00PM (± 1 hour) Monday-Friday. The EX group did not perform any additional exercise outside of this prescribed program during the 12 weeks. The participants in the CON group did not participate in the exercise intervention, or any outside exercise during the 12-week period, but were present and supervised in the laboratory at the same frequency, duration, and time of day as the EX group throughout the entire study period. Both groups of participants were advised weekly not to change their diet habits (~1920 kcal/day) for the duration of the study, and diet logs were obtained every week to keep track of dietary intake. Water intake was not recorded, however, participants were encouraged to consume approximately 2.5 liters of water per day (Sawka et

al. 2005). All exercise sessions were supervised by trained professionals and all measurements were taken by qualified researchers.

Blood sampling and analysis

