The Shapiro-Wilk test was used to determine the normality of the data. Independent t-tests were used to determine baseline differences between the two groups. A two-way analysis of variance (ANOVA) with repeated measures [group (CON and EX) x time (before and after 12 weeks)] was used to compare the difference of changes between pre- and post-jump rope exercise program within and between groups on the dependent variables. Bonferroni correction was used to determine the effects of the jump rope training program over time. When a significant main effect or interaction was noted, paired t-tests were used for post-hoc comparisons. An effect size analysis was performed using eta-squared (η^2) for the two-way ANOVA, and interpreted 0.01, 0.06, and 0.14 as small, medium and large, respectively (Lee et al. 2018). Cohen's d was used for the t-tests, interpreted as 0.20, 0.50, and 0.80 as small, medium and large, respectively (Lee et al. 2018). All analyses were performed using SPSS 25.0 (SPSS Inc., Chicago, IL, USA). Data are presented as Mean \pm SD. Statistical significance was set at $P \leq 0.05$. It was estimated that 40 participants would enable 80% power to detect a 5% decrease in baPWV after the jump rope exercise program based on previous literature (Figueroa et al. 2011).

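### The plan does not make the group-by-time interaction decisive, and it lets a time effect shared by both arms open pre-post paired t-tests that cannot compare EX with CON

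*Combined protocol and SAP*

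**What the plan says.** The section headed Statistical analysis plan specifies a two-way repeated-measures ANOVA with factors group (CON, EX) and time (before, after 12 weeks). Its stated purpose is "to compare the difference of changes between pre- and post-jump rope exercise program within and between groups". The follow-up rule is: "When a significant main effect or interaction was noted, paired t-tests were used for post-hoc comparisons".

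Three other sentences in that section bear on the point:

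- The only t-test between arms is for baseline: "Independent t-tests were used to determine baseline differences between the two groups".
- The multiplicity sentence refers to change over time and does not list the comparisons it covers: "Bonferroni correction was used to determine the effects of the jump rope training program over time".
- The power sentence claims "80% power to detect a 5% decrease in baPWV after the jump rope exercise program" and does not say whether the decrease is within EX or relative to CON.

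No other section gives a decision rule or names a primary analysis.

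**The concern.** In a trial with two arms and two time points, the exercise effect is the difference between the arms in their change. The interaction tests exactly that. A time main effect averages the change over both arms, and a group main effect averages baseline and week 12 within each arm. Neither isolates what exercise did, yet either one triggers the follow-up tests.

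Those follow-up tests are paired. Different girls are in each arm and no pairing between arms is defined, so a paired test can only compare before with after. The natural display is then one p-value for EX and one for CON. Reading significant in EX and not in CON as benefit compares two p-values instead of testing the difference. It can mislead in two ways: chance can push one arm over the line when both share a trend, and a real benefit can be hidden when the trend makes both arms significant.

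A shared trend is possible here. The Participants section says "All participants were classified as prehypertensive", and girls were also selected on waist and BMI, so regression to the mean can affect those variables. Under Study design, the control girls "were present and supervised in the laboratory at the same frequency, duration, and time of day as the EX group", so any effect of attendance would reach both arms. baPWV, the outcome in the power sentence, was not a selection variable.

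**Working it through.** **The plan's own figure.** The power claim (40 girls, 80%, 5% decrease) cannot be reproduced, because no SD is given. At two-sided 0.05 it needs an SD of 5.5% of baseline for a comparison of 20 with 20 (t-based), or an SD of change of 7.6% for a paired test within EX alone. The sentence fits either, so it does not show which test was meant to decide.

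**Inputs from the documents.** 20 per arm, two time points, significance level 0.05, trigger as quoted.

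**Assumptions.** Two-sided tests, normal data, SD of change set to 1, pre-post correlation 0.5, and a true mean change d (in SD of change) that is the same in both arms. This means no exercise effect.

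**Formulas.** With mean changes D_EX and D_CON, and s the pooled SD of change:

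- Interaction: t = (D_EX − D_CON) / (s√(2/20)), 38 df. The drift d cancels.
- Time effect: t = (D_EX + D_CON) / (s√(2/20)), 38 df. The drift enters twice.
- Paired test in one arm: t = D / (s_arm/√20), 19 df, noncentrality d√20.

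**Hand check.** At d = 0.5 the noncentrality is 0.5 × 4.472 = 2.236, and the paired test is significant with probability p = 0.5645. The arms are independent, so EX significant and CON not has probability p(1 − p) = 0.5645 × 0.4355 = 0.246 before the trigger is applied. At d = 0.8 the noncentrality is 3.578, p = 0.924 and p(1 − p) = 0.070. The trigger (time, group or interaction significant) trims these slightly. Simulation gives 23.7% and 7.0%.

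**Simulation with no exercise effect, 400,000 trials per scenario.** *EX only* means that the trigger is met, EX improves significantly and CON does not change significantly.

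| Favourable shared drift (SD of change) | 0 | 0.1 | 0.3 | 0.5 | 0.8 | 1.0 |
|---|---|---|---|---|---|---|
| *EX only*, trigger as written (%) | 1.5 | 4.0 | 15.7 | 23.7 | 7.0 | 1.1 |
| Interaction wrongly favours EX (%) | 2.5 | 2.5 | 2.5 | 2.5 | 2.5 | 2.5 |
| *EX only*, interaction as sole trigger (%) | 0.8 | 1.3 | 2.2 | 2.3 | 1.2 | 0.4 |
| *EX only*, trigger as written, paired tests at 0.025 (%) | 1.0 | 2.7 | 12.5 | 24.3 | 11.8 | 2.6 |

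- The first row passes 2.5% only between about 0.05 and 0.92 SD.
- At 0.5 SD, 21.4% of all trials show *EX only* with a non-significant interaction.
- With unfavourable drift of 0.1 / 0.3 / 0.5 SD, false benefit falls to 0.5 / 0.03 / 0.0%.
- A pre-post correlation of 0.7 gives 1.5 / 16.0 / 23.3 / 6.9% at drift 0 / 0.3 / 0.5 / 0.8, so that assumption matters little.
- The last row treats Bonferroni as halving 0.05 over the two paired tests. It does not remove the excess.

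**With a true effect of 0.9 SD (assumed; 200,000 trials per scenario).** The interaction has noncentrality 0.9/√(2/20) = 2.846 and power of 79% at any drift.

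| Favourable shared drift (SD of change) | 0 | 0.3 | 0.5 | 0.8 |
|---|---|---|---|---|
| *EX only* (%) | 90.3 | 75.2 | 43.5 | 7.6 |
| Both arms significant (%) | 4.8 | 24.7 | 56.5 | 92.4 |
| Interaction significant (%) | 79.2 | 79.2 | 79.1 | 79.2 |

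**The case against.** The strongest reply is that the right test is already in the plan. Comparing the difference of changes between groups describes the interaction, the ANOVA has its own effect-size scale ("An effect size analysis was performed using eta-squared"), and the paired tests are labelled post-hoc. With one degree of freedom the interaction needs no further between-arm test, and paired tests after a significant interaction are an ordinary description of where the change lies. On this reading, the error rates above belong to a misreading that the plan never endorses.

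Much of that stands. The absence of a 12-week between-arm t-test is not a fault in itself, and the rates are not properties of a stated decision rule. They also depend on drift that the documents do not size. With no drift the pattern is rarer than a false interaction, and at small drift a real effect produces *EX only* more often than it produces a significant interaction. Masking appears only from about 0.3 SD upward. Equal attendance is a control for attention, and nothing shows that attendance alone changes any outcome.

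What does not stand is that the wording is therefore harmless. The stated purpose covers change within groups as well as between them, no effect is made decisive, and a main effect has the same standing as the interaction in opening the paired tests. That is a stated rule, not an omission.

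**Conclusion.** The concern holds. The trigger as written lets a change common to both arms lead to tests that cannot answer the trial's question, and nothing elsewhere makes the interaction decide. The plan permits, but does not state, the inference from significant in EX and not in CON.

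If that inference were drawn, false benefit could reach about 24% against 2.5% for the interaction. This requires a favourable drift near 0.5 SD of change, and the excess vanishes outside roughly 0.05 to 0.92 SD. The size rests on assumed drift and normal data; the fault in the trigger does not. Regression to the mean makes drift most plausible for BP, waist and BMI, and that argument does not extend to baPWV. The documents report no results, so they do not show that any conclusion was drawn this way. It should be fixed.

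**What to change.** In the Statistical analysis plan:

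1. State that the exercise effect is judged only by the between-group contrast. This is the planned group-by-time interaction or, as an option, the group term of an ANCOVA adjusted for baseline. Report EX minus CON with a 95% CI.
2. Remove main effects as a trigger for the paired t-tests.
3. Label the within-arm paired t-tests and their Cohen's d as descriptive, and draw no efficacy conclusion from them.

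The cost is wording only. The interaction is already in the model, baseline values were collected, and no new data are needed. The price is that some significant within-arm results would no longer count as evidence of benefit. Because the document is written in the past tense, the change governs reporting and interpretation and cannot be presented as pre-specified.

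### Size-of-effect labels are attached to d from paired pre-post tests, and no between-arm estimate with a confidence interval is planned, so a change shared by both arms can be labelled a large effect.

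*Combined protocol and SAP*

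**What the plan says.** All of this is in the Statistical analysis plan section of the combined document; only the arm sizes come from Study design.

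- The main model is a repeated-measures ANOVA with factors "group (CON and EX) x time (before and after 12 weeks".
- If a main effect or the interaction is significant, "paired t-tests were used for post-hoc comparisons". Either main effect is enough to open this step; a significant interaction is not required.
- Two labelling rules follow. Eta-squared is used "for the two-way ANOVA, and interpreted 0.01, 0.06, and 0.14 as small, medium and large, respectively". Cohen's "d was used for the t-tests, interpreted as 0.20, 0.50, and 0.80 as small, medium and large". The plan does not say whether eta-squared is classical or partial, which ANOVA term it describes, or which SD is the divisor of d.
- The only between-arm t-tests named are those for baseline differences. Results are to be shown as mean and SD. No between-arm difference in change, and no confidence interval, is named.
- On sizing: "It was estimated that 40 participants would enable 80% power to detect a 5% decrease in baPWV after the jump rope exercise program". For support, the sentence points only to a published source. No SD, pre-post correlation, test or contrast is given. The arms are "exercise group (EX, n = 20) or the control group (CON, n = 20").

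**The concern.** The trial randomises girls to EX or CON so that change in EX can be set against change in CON. The d rule does not do that. A paired test compares the same girls before and after, so its d includes everything that moved over 12 weeks: growth, familiarity with the measurements, season, regression to the mean after selection on raised blood pressure, and exercise. Study design has CON attend the laboratory on the same schedule as EX, so the design itself provides for shared influences to be subtracted out. A d taken within EX puts them back.

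The labels matter because they are the plan's only stated rule for describing how big an effect is. A report that follows the plan could describe a large effect in EX when the between-arm comparison shows none. It could also choose its eta-squared label through the variant printed.

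**Working it through.** **The plan's own figure.** The 40 participants for 80% power cannot be reproduced, because no SD, correlation or test is stated. It can only be solved backwards under an assumption. With 20 v 20, a two-sided 0.05 level (sidedness is not stated), no dropout, and sizing on the between-arm difference in change, the noncentral t on 38 df gives 80% power at 0.909 SD of change (noncentrality 0.909 × √(20/2) = 2.87). A 5% fall would then imply an SD of change of about 5/0.909 = 5.5% of baseline.

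**Check 1: what a paired d shows when exercise has no effect.**

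Inputs: 20 per arm (Study design); 0.05 level and post-hoc trigger (Statistical analysis plan). Assumed: both arms change by 0.8 SD of change, normal data, and d = mean change / SD of change.

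- *Does the post-hoc step open?* The time effect pools 40 girls: noncentrality 0.8 × √40 = 5.06, against a critical t of 2.024 on 38 df. Probability 0.998, so over 99%.
- *Is the interaction significant?* The true between-arm difference is 0, so about 5%, by construction.
- *Is d in EX labelled large?* d ≥ 0.80 means t ≥ 0.80 × √20 = 3.58 on 19 df with noncentrality 3.58. Probability 0.52.
- *Is it at least medium?* d ≥ 0.50 means t ≥ 0.50 × √20 = 2.24. Probability 0.90.

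Simulation with the post-hoc trigger applied gives the same figures: about 52% and 90%.

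The divisor matters. With the raw outcome SD instead, d = 0.8 × √(2(1 − r)), where r is the pre-post correlation. This is 0.80 at r = 0.5 and 0.51 at r = 0.8. The label moves, but the quantity is still a within-arm change.

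**Check 2: does the eta-squared variant matter?**

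Take raw SD 1, no change in CON, and change D in EX. The sums of squares are:

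- interaction = 80 × (D/4)² = 5D², with group and time each the same;
- error within girls = 38(1 − r), and between girls = 38(1 + r), together 76.

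So classical eta-squared = 5D²/(15D² + 76), and partial eta-squared = 5D²/(5D² + 38(1 − r)). For the back-solved effect, D = 0.909 × √(2(1 − r)):

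| assumed r | D | classical | partial |
|---|---|---|---|
| 0.5 | 0.909 | 0.047 | 0.179 |
| 0.7 | 0.704 | 0.030 | 0.179 |
| 0.8 | 0.575 | 0.020 | 0.179 |
| 0.9 | 0.407 | 0.011 | 0.179 |

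At r = 0.5, for example: 5D² = 4.13, so classical = 4.13/(12.40 + 76) = 0.047 and partial = 4.13/(4.13 + 19) = 0.179. Against the plan's cut-offs, every classical value in the table is *small* and every partial value is *large*. Outside this range the classical label changes: it is *medium* below r of about 0.33, and it falls under the *small* cut-off above about 0.905.

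**The case against.** The strongest reply is that the labels are descriptive. Inference rests on the group-by-time ANOVA at the 0.05 level; no test, error rate, power or sample size changes with the labels. The benchmarks are conventional and referenced, and naming the variant and the SD would remove the ambiguity. Most of this stands, and it limits the point to interpretation. Deleting the benchmarks would be a matter of preference. It does not answer Check 1: a fully defined paired d still does not compare EX with CON.

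Three stronger readings are tempting, and the documents do not support them.

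- *That the plan labels its own target effect small by one rule and large by the other.* This needs four things the documents do not give: sizing on the between-arm change, classical eta-squared, d on the SD of change, and r between about 0.33 and 0.905. With partial eta-squared both rules say *large*. If the trial was sized on a paired test in EX (n = 20), d is 0.66 and partial eta-squared 0.103, both *medium*. If it was sized on a paired test in all 40, they are 0.45 and 0.052, both *small*.
- *That classical eta-squared shrinks as the pre-post correlation rises, whatever the treatment effect.* The formula above contains no r. With D held at 0.909 it is 0.047 at every r. It falls down the table only because D itself falls from 0.909 to 0.407. At fixed D it is partial eta-squared that moves: 0.18, 0.27, 0.35 and 0.52 at r = 0.5, 0.7, 0.8 and 0.9.
- *That with no change in either arm, chance alone puts paired d at 0.20 or more in 38% of trials.* That ignores the rule that paired tests follow a significant ANOVA term. With the rule applied, d in EX does so in about 10%.

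**Conclusion.** The point holds as a matter of interpretation and should be corrected. The plan's d rule measures within-arm change, opens on a main effect alone, and has no between-arm estimate with an interval beside it. With an equal change of 0.8 SD of change in both arms, it labels EX *large* in about 52% of trials although exercise adds nothing.

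That figure rests on the assumed shared change, on normal data and on d using the SD of change. It illustrates what the rule allows and does not predict this trial's data. The structural point needs none of these assumptions.

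The undefined eta-squared is a lesser, related gap. Under the stated sizing assumption the label can be *large* or *small* depending on the variant printed. The documents do not show that such a conflict will occur.

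**What to change.** For each outcome:

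- Report the between-arm difference in 12-week change, or its baseline-adjusted form, as the effect of exercise. Give it in original units and as a percentage of the baseline mean, with a 95% CI. The percentage scale lets the baPWV result be read against the 5% in the sizing statement.
- If a standardised size is wanted, divide that difference by the pooled baseline SD and give its CI.
- Do not present within-arm d as the effect of exercise. If paired results are shown, describe them as change within an arm.
- If eta-squared is kept, name the variant and report it for the group-by-time term.

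This uses data the design already collects. It costs a few sentences in the Statistical analysis plan and one table column. The downside is that descriptions of the effect may become less flattering.
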